1 SYNOPSIS

Title: A Randomized, Double-Blind, Placebo-Controlled, Phase 3 Study of Navitoclax in Combination with Ruxolitinib Versus Ruxolitinib in Subjects with Myelofibrosis (TRANSFORM-1)	
Background and Rationale:	
Current therapies, other than hematopoietic stem cell transplantation (HSCT), are not able to control all the clinical manifestations of myelofibrosis (MF).
 
Navitoclax binds to and inhibits antiapoptotic B-cell lymphoma-2 (BCL-2) family proteins with high affinity. Thus, it selectively induces program death in cells that have a BCL-2 protein ratio shifted towards survival as observed in human cell lines derived from small cell lung carcinomas and lymphoid malignancies. Additionally, navitoclax potently enhances the cytotoxicity of both chemotherapy and radiation in cells derived from multiple, major tumor types, regardless of whether single-agent efficacy is achieved.
 
Preclinical data suggest that the combination of navitoclax and ruxolitinib may provide disease-modifying therapy in subjects with primary and secondary MF. Preliminary clinical data from Study M16-109 of navitoclax and ruxolitinib in subjects with primary and secondary MF who have previously received ruxolitinib suggest favorable spleen response rates and an acceptable safety profile. Best on study spleen volume reductions of > 35% have been observed in 43% of subjects, with 35% of subjects also achieving a reduction of > 50% in total symptom scores. The response rates of the combination of navitoclax and ruxolitinib in subjects previously treated with ruxolitinib are comparable to those observed with both ruxolitinib and fedratinib in patients who were not previously treated.
 
This double-blind, Phase 3 study will evaluate the combination of navitoclax and ruxolitinib versus ruxolitinib in adult subjects with primary or secondary MF who have not previously received a Janus kinase 2 (JAK2) inhibitor.

Objective(s) and Endpoint(s):	
Objectives
 
The primary objective is to evaluate the effect of navitoclax in combination with ruxolitinib on splenomegaly response when compared to ruxolitinib in subjects with MF.
 
The secondary objectives are:
 
 • To evaluate the effect of navitoclax in combination with ruxolitinib on the onset, magnitude, and duration of disease response, including total symptom score (TSS), effects on spleen, bone marrow fibrosis, and anemia. • To evaluate the effect of navitoclax in combination with ruxolitinib on measures of health-related quality of life (HRQoL), including fatigue, and physical functioning. • To evaluate the effect of navitoclax in combination with ruxolitinib on overall survival (OS) and leukemia-free survival (LFS).

	
The exploratory objectives are:
 
 • To evaluate responses to navitoclax and ruxolitinib versus ruxolitinib in subjects with high molecular risk (HMR) mutations. • To evaluate the effect of navitoclax in combination with ruxolitinib on progression-free survival (PFS). • To evaluate the effect of navitoclax in combination with ruxolitinib on the frequency of mutated alleles. • Exploration of biomarkers predictive of navitoclax activity and response may be performed. Potential analysis may include, but will not be limited to, the evaluation of: 
 • BCL-2 family profiling • Inflammatory cytokine reduction • Mutational status. 
Endpoints
 
Primary Efficacy Endpoint:
 
 • At least 35% reduction in spleen volume at Week 24 from baseline (SVR_{35W24}) as measured by magnetic resonance imaging (MRI) or computed tomography (CT) scan, per International Working Group (IWG) criteria. 
Secondary Efficacy Endpoints:
 
 • Change in total symptom score (TSS) at Week 24 from baseline as measured by Myelofibrosis Symptom Assessment Form (MFSAF) v4.0 • At least 35% reduction in spleen volume from baseline (SVR₃₅) as measured by MRI or CT scan, per IWG criteria • Duration of SVR₃₅ • Change in fatigue at Week 24 from baseline as measured by the PROMIS Fatigue SF 7a • Change in physical functioning at Week 24 from baseline, as measured by the Physical functioning domain of the European Organisation for Research and Treatment of Cancer (EORTC) Quality of Life questionnaire (QLQ)-C30 • Anemia response per IWG criteria • Overall survival • Leukemia-free survival • Reduction in grade of bone marrow fibrosis from baseline as measured by the European consensus grading system 
Exploratory Endpoints:
 
 • At least 50% reduction in palpable splenomegaly from baseline per IWG criteria • Red blood cell (RBC) transfusion during study drug treatment
--	---

	
 • Change in quality of life from baseline as measured by the global health status/quality of life domain of the EORTC QLQ-C30 • Change in the summary score for the EORTC QLQ-C30 from baseline • Progression-free survival per IWG criteria • Change in frequency of allelic mutations from baseline • Change in EQ-5D-5L from baseline • Change in impacts associated with fatigue from baseline as assessed by the PROMIS Fatigue 7a impact items • Change in fatigue-related symptoms from baseline as assessed by the PROMIS Fatigue 7a symptom items • Translational biomarkers and correlation with clinical outcomes • Overall response of clinical improvement per IWG criteria • At least 50% reduction in TSS at Week 24 from baseline (TSS_{50W24}) • Time to first TSS₅₀ • Duration of TSS₅₀ • TSS response rate at any time based on meaningful change threshold (MCT) • Time to first TSS response • Duration of TSS response 
Safety Endpoints: Safety endpoints will be based on the following evaluations: adverse event (AE) monitoring, physical examinations, vital sign measurements, electrocardiogram (ECG) variables, and clinical laboratory testing (hematology and chemistry).
 
Pharmacokinetic Endpoints: Sparse pharmacokinetic (PK) samples will be collected at specified time points. Individual plasma concentrations of navitoclax from sparse PK sampling will be tabulated and summarized. Population PK parameters of navitoclax such as apparent oral clearance (CL/F) and apparent volume of distribution (V/F) may be estimated using non-linear mixed effects model.
 
Biomarker Endpoints: Biospecimens (whole blood, plasma, bone marrow aspirate, and/or bone marrow core) will be collected at specified time points throughout the study to evaluate known and/or novel disease-related or drug-related biomarkers in circulation or at tissue sites. Some of these samples may be optional. Types of biomarkers may include nucleic acids, proteins, lipids, and/or metabolites, either free or in association with particular cell types. The analyses may include but are not limited to mutational status, BCL-2 family profiling, and inflammatory cytokine reduction.

--	--

Investigator(s):	Multicenter
Study Site(s):	Approximately 190 sites in approximately 26 countries
Study Population and Number of Subjects to be Enrolled:	Approximately 230 adult subjects with intermediate-2 or high-risk MF who have not been previously treated with JAK2 inhibitor therapy.
Investigational Plan:	
This is a Phase 3, double-blind, placebo-controlled, randomized, 2-arm study of the combination of navitoclax and ruxolitinib compared to ruxolitinib in subjects with MF who have not previously received JAK2 inhibitors.
 
Approximately 230 subjects will receive either navitoclax once daily and ruxolitinib twice daily (Arm A), or placebo once daily and ruxolitinib twice daily (Arm B, control) until end of clinical benefit or occurrence of unacceptable toxicity or discontinuation criteria have been met. Stratification will be based on intermediate-2 versus high risk (Dynamic International Prognostic Scoring System Plus [DIPSS+]) and platelet count $\leq 200 \times 10^9/L$ versus $> 200 \times 10^9/L$.

Key Eligibility Criteria:	
 • Subject ≥ 18 years of age. • Subject with a documented diagnosis of primary MF as defined by the World Health Organization classification or secondary MF (post polycythemia vera [PPV]-MF or post essential thrombocythemia [PET]-MF) • Subject must be able to complete the MFSAF v4.0 on at least 4 out of the 7 days immediately preceding the date of randomization. 
 • Subject has at least 2 symptoms with a score ≥ 3 or a total score of ≥ 12, as measured by the MFSAF v4.0. • Subject classified as intermediate-2 or high-risk MF as defined by the Dynamic International Prognostic Scoring System Plus (DIPSS+). • Subject must not have received prior treatment with a JAK2 inhibitor. • Subject must not have received prior treatment with a B-cell lymphoma 2 homology 3 (BH3) -mimetic compound, bromodomain and extra-terminal motif (BET) inhibitor or stem cell transplant. • Subject has splenomegaly defined as spleen palpation measurement ≥ 5 cm below costal margin or spleen volume ≥ 450 cm³ as assessed centrally by MRI or CT scan. • Subject must be ineligible for stem cell transplantation at time of study entry due to age, comorbidities, or unfit for unrelated or unmatched donor transplant and other criteria per National Comprehensive Cancer Network guidelines. • Subject with an Eastern Cooperative Oncology Group (ECOG) performance status of 0, 1, or 2. • Subject must not receive medication that interferes with coagulation or platelet function within 3 days prior to the first

	
dose of study drug or during the study treatment period except for low dose aspirin (up to 100 mg daily) and low molecular weight heparin (LMWH).


Study Drug and Duration of Treatment:
	
Navitoclax/placebo will be provided as film-coated tablets (25 mg and 100 mg) for oral administration. Ruxolitinib tablets will be provided by AbbVie or sourced locally by the sites, depending on country regulations.
 
 • Arm A - Experimental group: navitoclax + ruxolitinib • Arm B – Control group: placebo to match navitoclax + ruxolitinib 
Dosing of study drugs:
 
 • Navitoclax/placebo: 
 • Platelet count $> 150 \times 10^9/L$: 200 mg once daily starting dose • Platelet count $\leq 150 \times 10^9/L$: 100 mg once daily starting dose; escalate to 200 mg once daily after ≥ 7 days, if tolerable (platelets $\geq 75 \times 10^9/L$). • After the Week 25 Day 1 visit, dose may be increased to 300 mg once daily at the discretion of the investigator based on platelet count for subjects with sub-optimal spleen response defined as failure to achieve a spleen volume reduction of at least 10%. • Ruxolitinib (administered per USPI/SmPC/local prescribing guidance): 
 • Platelet count $> 200 \times 10^9/L$: 20 mg twice daily starting dose • Platelet count $100 \times 10^9/L$ to $200 \times 10^9/L$: 15 mg twice daily starting dose. • Ruxolitinib dose adjustment in subjects with hepatic or renal impairment should be determined per local label/prescribing guidance. 
Treatment may continue until end of clinical benefit or occurrence of unacceptable toxicity or discontinuation criteria have been met.

Date of Protocol Synopsis:
	
23 March 2023

2 INTRODUCTION

2.1 Background and Rationale

Why Is This Study Being Conducted

Myelofibrosis (MF) is an acquired clonal Philadelphia chromosome negative myeloproliferative neoplasm that is characterized by constitutional symptoms, splenomegaly, an increased risk of transformation to acute myeloid leukemia, and a shortened life expectancy.¹ Although Janus kinase 2 (JAK2) inhibitors such as ruxolitinib are approved in several geographic regions, these therapies are insufficient for most patients and better treatments are needed. Whilst therapy with ruxolitinib induces improvement in splenomegaly and disease-related symptoms, it does not eradicate the malignant clones and may induce modest improvement in the degree of bone marrow fibrosis in a small subset of patients treated.^{2,3} Patients who stop ruxolitinib rapidly become symptomatic, some patients do not respond to ruxolitinib, and others develop secondary resistance, thus ruxolitinib alone is typically insufficient for sustained disease control.⁴ Current therapies, other than hematopoietic stem cell transplantation (HSCT) which is only accessible to 5 to 10% of patients, are not able to control all the clinical manifestations of MF. Therefore, new treatments including combination therapies with ruxolitinib as the backbone may provide additional benefits and improve clinical outcomes in these patients.

Navitoclax binds to and inhibits antiapoptotic B-cell lymphoma-2 (BCL-2) family proteins with high affinity to BCL-X_L, BCL-2 and BCL-W. Thus, it selectively induces program death in cells that have a BCL-2 family protein ratio shifted towards survival as observed in human cell lines derived from small cell lung carcinomas and lymphoid malignancies (concentration required for 50% effect [EC₅₀] ≤ 1 μM). Additionally, navitoclax potently enhances the cytotoxicity of both chemotherapy and radiation in cells derived from multiple, major tumor types, regardless of whether single-agent efficacy is achieved.

Clinical studies conducted to date have assessed safety, pharmacokinetics, and initial efficacy of navitoclax as a single agent and as combination therapy in subjects with hematological malignancies and subjects with solid tumors. The monotherapy recommended Phase 2 dose (RPTD) has been determined as 250 mg in chronic lymphocytic leukemia (CLL) (with a 100 mg lead-in period prior to Cycle 1) and 325 mg under the continuous dosing schedule in small cell lung cancer and other lymphoid malignancies (excluding CLL; with a 150 mg lead-in period prior to Cycle 1), although the starting dose was reduced to 250 mg in lymphoid malignancies as this was found to be more tolerable.⁵⁻⁸

Preclinical data suggest that navitoclax may overcome JAK2 resistance, resensitizing cells to JAK2 inhibition from ruxolitinib, and therefore may provide disease-modifying therapy in subjects with primary myelofibrosis (PMF) and secondary myelofibrosis (SMF).⁶ The combination of navitoclax and ruxolitinib in subjects with MF (Study M16-109) has demonstrated efficacy in subjects with persistent splenomegaly while receiving treatment with ruxolitinib for at least 12 weeks (AbbVie data on file). The median duration of prior ruxolitinib exposure before initiating navitoclax on Study M16-109 was 21 months (range 4 to 71 months). After 24 weeks of treatment with navitoclax and ruxolitinib, 30% of subjects achieved spleen volume reduction ≥ 35% (SVR₃₅). Additionally, spleen responses seem to deepen beyond 24 weeks of treatment, and the best overall SVR₃₅ was further improved to 43%. Symptom improvements were reported in 65% of subjects with 35% of subjects achieving ≥ 50%

reduction from baseline in total symptom score at Week 24. Additionally, reductions in bone marrow fibrosis of ≥ 1 grade were observed in 27% of subjects, suggesting this drug combination may be disease modifying. The safety profile was acceptable with the most common Grade ≥ 3 treatment-emergent AEs reported as thrombocytopenia and anemia. There were no serious adverse events of bleeding. There was 1 treatment-emergent death due to pneumonia that was assessed by the investigator as having no reasonable possibility of relationship to navitoclax.

Preliminary pharmacokinetic (PK) data from the Phase 2 M16-109 study of the combination of navitoclax and ruxolitinib in subjects with PMF and SMF who have previously received ruxolitinib showed that upon co-administration, navitoclax exposures ($n = 34$) were comparable to historical data in non-MF patient population, while ruxolitinib area under the curve from 0 to 12 hours (AUC_{0-12}) ($n = 28$) was 29% lower compared to historical data in MF patients. The impact of navitoclax on ruxolitinib exposures is being evaluated in Study M16-109.

Preliminary data in the Phase 2 M16-109 study of the combination of navitoclax and ruxolitinib in subjects with PMF and SMF who have previously received ruxolitinib suggest favorable spleen response rates and an acceptable safety profile. Best on study spleen volume reductions of $> 35\%$ have been observed in 43% of subjects, with 35% of subjects also achieving a reduction of $> 50\%$ in total symptom scores.⁹ The response rates of the combination of navitoclax and ruxolitinib in subjects previously treated with ruxolitinib are comparable to those observed with both ruxolitinib and fedratinib in patients not previously treated.² These data support further evaluation of this combination in patients with MF that have not received prior treatment with a JAK2 inhibitor. This Phase 3 study is designed to evaluate the combination of navitoclax and ruxolitinib versus ruxolitinib in subjects with PMF or SMF who have not previously received a JAK2 inhibitor.

Clinical Hypothesis

Navitoclax, when combined with ruxolitinib, is reasonably likely to result in higher SVR₃₅ rates that are more durable, greater reductions in total symptom score (TSS), reversal of bone marrow fibrosis, and more allelic burden reductions than the current standard treatment, ruxolitinib alone.

2.2 Benefits and Risks to Subjects

Ruxolitinib (a dual Janus kinase 1 [JAK1] and JAK2 inhibitor) and fedratinib (dual JAK2 and FMS-like tyrosine kinase 3 [FLT3] inhibitor) are approved by numerous regulatory bodies worldwide for the treatment of myelofibrosis. While the approval of these JAK2 inhibitors has changed the treatment landscape for patients with myelofibrosis, their therapeutic remit is aimed at improving symptoms and quality of life. The only treatment modality capable of curing MF is allogeneic HSCT. The applicability of HSCT is limited by the inherent risks in this population, with their attendant comorbidities.

Preclinical data suggest that the combination of navitoclax with ruxolitinib may provide disease-modifying therapy for patients with PMF or SMF. Clinical studies (single-agent and combination therapy) have assessed the safety, pharmacokinetics and initial efficacy in subjects with hematologic malignancies or in subject with solid tumors.

Risks observed in nonclinical and/or clinical studies associated with navitoclax administration are thrombocytopenia, lymphopenia, and neutropenia. Thrombocytopenia has been the primary

dose-limiting toxicity. Navitoclax accelerates apoptosis, rather than lysis, of circulating mature platelets whether endogenous or transfused. This mechanism of action differs from the thrombocytopenia caused by conventional chemotherapy (i.e., toxicity to platelets progenitors in the bone marrow) and should, therefore, be managed. Actions are in place in study protocols to mitigate these risks and, when medically indicated, to treat these effects; these include appropriate patient selection, careful monitoring, and treatment management guidelines.

The most common treatment emergent hematological adverse reactions of any grade with an incidence > 10% reported with navitoclax in combination with ruxolitinib (Study M16-109; Cohort 3) in patients with MF who have not previously received ruxolitinib are thrombocytopenia, neutropenia, and anemia. The most common treatment emergent nonhematological adverse reactions of any grade with an incidence \geq 10% are nausea and diarrhea.

The most common hematological adverse reactions with an incidence > 20% reported with ruxolitinib monotherapy in patients treated for MF are thrombocytopenia and anemia. The most common nonhematological adverse reactions with an incidence \geq 15% are bruising, dizziness, headache, and diarrhea. Non-melanoma skin cancers including basal cell, squamous cell, and Merkel cell carcinoma have also been reported requiring periodic skin examination.

The preliminary data of the combination of navitoclax and ruxolitinib (Study M16-109) in patients with MF who have previously received ruxolitinib for at least 12 weeks with persistent splenomegaly are favorable, demonstrating improvement in spleen volume reduction and total symptom score along with reduction in bone marrow fibrosis after treatment with current standard of care, and support further evaluation of the combination in patients with MF who have not received prior treatment with a JAK2 inhibitor.

The Sponsor has evaluated the potential risks of study participation during a global or regional epidemic or other extreme circumstance and concludes that the potential benefit of the study treatment outweighs the additional risk.

For further benefit and risk details, please see the current navitoclax Investigator's Brochure.

Considering the coronavirus disease 2019 (COVID-19) pandemic, the benefit and risk to subjects participating in this study has been re-evaluated. Subjects receiving navitoclax may be at an increased risk for COVID-19 infection or experience serious illness if infected. Management of these adverse events will be made on a case-by-case basis with consideration of benefit/risk by the investigators. However, based on the population, the disease being studied, and the anticipation that COVID-19 related risks are unknown between study subjects and the broader population of subjects receiving treatment for myeloproliferative neoplasms, no known change to the benefit/risk balance for subjects in this study is expected.

3 OBJECTIVES AND ENDPOINTS

Primary Objective

1. To evaluate the effect of navitoclax in combination with ruxolitinib on splenomegaly response when compared to ruxolitinib in subjects with myelofibrosis (MF).

Secondary Objectives

1. To evaluate the effect of navitoclax in combination with ruxolitinib on the onset, magnitude, and duration of disease response, including total symptom score (TSS), effects on spleen, bone marrow fibrosis, and anemia.
2. To evaluate the effect of navitoclax in combination with ruxolitinib on measures of health-related quality of life (HRQoL) including fatigue, and physical functioning.
3. To evaluate the effect of navitoclax in combination with ruxolitinib on overall survival (OS) and leukemia-free survival (LFS).

Exploratory Objectives

1. To evaluate responses to navitoclax and ruxolitinib in subjects with high molecular risk (HMR) mutations.
2. To evaluate the effect of navitoclax in combination with ruxolitinib on progression-free survival (PFS).
3. To evaluate the effect of navitoclax in combination with ruxolitinib on the frequency of mutated alleles.
4. Exploration of biomarkers predictive of navitoclax activity and response may be performed. Potential analysis may include, but will not be limited to, the evaluation of:
 - BCL-2 family profiling
 - Inflammatory cytokine reduction
 - Mutational status.

3.1 Primary Endpoint

At least 35% reduction in spleen volume at Week 24 (SVR_{35W24}) from baseline as measured by magnetic resonance imaging (MRI) or computed tomography (CT) scan, per International Working Group (IWG) criteria.⁹

3.2 Secondary Endpoints

Secondary efficacy endpoints:

- Change in total symptom score (TSS) at Week 24 from baseline as measured by Myelofibrosis Symptom Assessment Form (MFSAF) v4.0
 - At least 35% reduction in spleen volume from baseline (SVR₃₅) as measured by MRI or CT scan, per IWG criteria
 - Duration of SVR₃₅
 - Change in fatigue at Week 24 from baseline, as measured by the PROMIS Fatigue SF 7a
-

- Change in physical functioning at Week 24 from baseline, as measured by the physical functioning domain of the European Organisation for Research and Treatment of Cancer (EORTC) quality of life questionnaire (QLQ)-C30
- Anemia response per IWG criteria
- Overall survival
- Leukemia-free survival
- Reduction in grade of bone marrow fibrosis from baseline as measured by the European consensus grading system¹⁰

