7.1 Demographics and Baseline Characteristics

All baseline characteristic summary statistics and analyses are based on characteristics prior to the first dose of study drug or date of randomization for untreated subjects.

Distributions of the continuous demographic and baseline characteristic variables will be summarized by treatment arms with the number of non-missing observations, mean, standard deviation, and median, as well as the minimum and maximum values.

For the categorical demographic and baseline characteristic variables, the frequency and percentages of subjects within each category will be summarized by treatment arms. The number of subjects with missing information will also be summarized.

The following demographic and baseline characteristics will be summarized:

Demographics

- Age (years) and Age Categories (18 - < 65, 65 - < 75, ≥ 75 years)
- Gender (Male, Female)
- Race (White, Black or African American, Asian, Other)
- Ethnicity (Hispanic or Latino, Not Hispanic or Latino)
- Region (US, Europe, Japan, Other Regions)
- Height (cm)
- Weight (kg)
- Body Mass Index (kg/m²)

Baseline and Disease-Related Characteristics

- DIPSS+ Risk Group Reported in IRT (Intermediate-2, High)
- DIPSS+ Risk Group Reported in EDC (Intermediate-1, Intermediate-2, High)

- Platelet Count Reported in IRT ($\leq 200 \times 10^9/L$, $> 200 \times 10^9/L$)
- Baseline Platelet Count ($\leq 200 \times 10^9/L$, $> 200 \times 10^9/L$)
- Type of Myelofibrosis (Primary Myelofibrosis, Secondary Myelofibrosis)
 - Type of Secondary Myelofibrosis (Post-Polycythemia Vera Myelofibrosis, Post-Essential Thrombocythemia Myelofibrosis)
- JAK2 V617F Mutation (Detected, Not Detected)
- CALR Frameshift Mutation (Detected, Not Detected)
- MPL W515 Mutation (Detected, Not Detected)
- Negative of JAK2, CALR and MPL (Yes, No)
- High Molecular Risk (Yes, No)
- Time Since Myelofibrosis Diagnosis (months)
- Number of Prior Lines of Therapies for Myelofibrosis
- Reasons for Change of Therapy (Splenomegaly, Worsening Symptoms, Increased Need for Transfusion, Anemia, Thrombocytopenia, Increasing WBC, Increasing LDH, Other)
- Baseline ECOG Performance Status (0, 1, 2)
- Baseline Spleen Length by Palpation (cm)
- Baseline Spleen Volume (cm^3)
- Baseline TSS score
- Baseline Bone Marrow Fibrosis Grade (MF-0, MF-1, MF-2, MF-3)
- Baseline Transfusion Dependent (Yes, No)
- Baseline Hemoglobin (g/dL)
- Baseline CTCAE Grade of Anemia
- Baseline Platelet Count ($10^9/L$)

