8.0 Efficacy Analyses

8.1 General Considerations

Unless otherwise specified, all randomized subjects in the ITT population will be included in the efficacy analyses. All statistical tests will be 2-sided at an alpha level of 0.05.

The primary analysis will be performed after all ongoing subjects have completed 24 weeks of follow-up and the database has been locked. Unless otherwise specified, data after the cutoff date will be excluded from statistical analyses.

Unless otherwise specified, all subjects will be analyzed according to the baseline platelet count and DIPSS+ score collected in Electronic Data Capture (EDC) system. For subjects with missing karyotype information, the DIPSS+ score will be calculated by assuming these subjects do not have unfavorable karyotype. The DIPSS+ score will be categorized by intermediate (including both intermediate-1 and intermediate-2) and high risk.

Unless otherwise specified, binary variables (e.g., response rates) will be analyzed using Cochran-Mantel-Haenszel (CMH) test, stratified by DIPSS+ risk group (intermediate versus high risk) and platelet count ($\leq 200 \times 10^9/L$ versus $> 200 \times 10^9/L$). The 95% confidence interval for the response rate will be provided for each treatment arm using the exact binomial distribution. The strata-adjusted difference in the response rates between the treatment arms and the 95% confidence interval for the difference will also be provided.

Unless otherwise specified, continuous data from patient-reported outcome will be analyzed using linear mixed effects model with treatment arm, visit, treatment by visit interaction, DIPSS+ risk group (intermediate versus high risk), platelet count ($\leq 200 \times 10^9/L$ versus $> 200 \times 10^9/L$) and baseline score as fixed effects. An unstructured variance covariance matrix will be used. The compound symmetry variance covariance matrix will be used if the model does not converge with the unstructured matrix. Change in score from baseline will be compared between the treatment arms for the specified post-baseline visit. The least-squares mean change from baseline and the corresponding 95% confidence interval will be provided for each treatment arm. In addition, the least-squares mean of the difference between the treatment arms and the corresponding 95% confidence interval will be provided.

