8.3.4 Additional Analyses of the Primary Efficacy Endpoint(s)

The following additional analyses will be performed for SVR_{35W24}:

- Percent change from baseline in spleen volume at Week 24 will be summarized for each treatment arm and presented graphically in waterfall plots.
- Sensitivity analysis of SVR_{35W24} will be performed by excluding subjects whose DIPSS+ risk group is intermediate-1.
- Spleen volume reduction at Week 24 will be descriptively summarized by the following categories: $\geq 10\%$ to $< 25\%$, $\geq 25\%$ to $< 35\%$, $\geq 35\%$ to $< 50\%$, and $\geq 50\%$.
- CMH test stratified by DIPSS+ risk group (intermediate-2 versus high risk) and platelet count ($\leq 200 \times 10^9/L$ versus $> 200 \times 10^9/L$) collected in IRT.
- Tipping point analysis as described in Section 8.2.

Logistic regression with model selection procedure using relevant demographic and baseline characteristics in Section 7.1 may be performed to evaluate the robustness of the primary analysis.

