8.4.1.6 Reduction in Grade of Bone Marrow Fibrosis from Baseline

Grade of bone marrow fibrosis will be measured by the European consensus grading system⁶ and assessed centrally. The proportion of subjects who achieve a reduction of at least 1 grade in bone marrow fibrosis from baseline will be analyzed using the statistical method described for binary variables in Section 8.1. Data after subjects have confirmed disease progression or started post-study treatment will be excluded from the analysis.

Subjects without any post-baseline grade of bone marrow fibrosis measurement will be treated as non-responders. Subjects who do not receive any study drug will be treated as non-responders. Subjects without baseline bone marrow fibrosis assessment will be treated as non-responders.

The analysis of reduction in grade of bone marrow fibrosis will be performed on subjects who have a bone marrow fibrosis grade determined at baseline and have at least one post-baseline assessment.

Time to first reduction in grade of bone marrow fibrosis from baseline will be descriptively summarized for each treatment arm. Reduction in grade of bone marrow fibrosis at Week 24 will be descriptively summarized.

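### The ranked marrow-fibrosis test does not adjust for baseline fibrosis grade; the test is valid, but if response varies with grade, adjustment could recover up to about 5 to 6 points of power in a test that gates OS, LFS, fatigue and physical functioning

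*Protocol*

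**What the plan says.** Protocol 3.2 lists the endpoint as "Reduction in grade of bone marrow fibrosis from baseline as measured by the European consensus grading system". SAP 8.4.1.6 makes it binary: the proportion with "a reduction of at least 1 grade in bone marrow fibrosis from baseline will be analyzed using the statistical method described for binary variables" in SAP 8.1. That method is a "Cochran-Mantel-Haenszel (CMH) test, stratified by DIPSS+ risk group (intermediate versus high risk) and platelet count" (200 × 10⁹/L as the cut).

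Randomization uses two similar factors (SAP 2.3). DIPSS+, as set out in Protocol Appendix F, contains no fibrosis grade. SAP 7.1 lists "Baseline Bone Marrow Fibrosis Grade (MF-0, MF-1, MF-2, MF-3" among the characteristics to be tabulated, but no analysis of the fibrosis endpoint adjusts for it and SAP 8.6 does not name it as a subgroup. The patient-reported continuous endpoints, by contrast, have "baseline score as fixed effects" (SAP 8.1). The one covariate model for a binary endpoint is optional and belongs to SVR35 at Week 24: "Logistic regression with model selection procedure using relevant demographic and baseline characteristics in Section 7.1 may be performed" (SAP 8.3.4).

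In SAP Table 1 fibrosis is rank 5, tested once at two-sided 0.05 at the Week 48 analysis. OS, LFS, fatigue and physical functioning follow at ranks 6 to 9. Protocol 7.6 gives the same order.

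**The concern.** Response is judged against each subject's own starting grade, so that grade is a natural candidate for a prognostic factor. At the extreme, a subject at MF-0 cannot respond at all. If response rates differ by grade, a two-factor CMH leaves that variation unexplained: the standard error is larger than it need be, and a chance difference between arms in grade mix carries into the estimated treatment difference.

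What raises the stakes is the position in the sequence. A non-significant fibrosis result blocks formal claims on four later endpoints, including survival. Neither document states a power, a control rate or an assumed effect for this test.

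**Working it through.** **Plan's own figure.** There is none to reproduce for fibrosis. The stated 90% power is for SVR35 at Week 24. Its treatment rate is redacted; 115 per arm against 40% gives 90% power at about 61.2%. The only fibrosis rate in the documents is 27% (Protocol 2.1), from an uncontrolled study in previously treated subjects and not split by baseline grade. The grade mix and the rates by grade below are therefore assumptions, shown as a range.

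**Step 1: size of chance imbalance.** With 115 per arm and an assumed half of subjects at MF-3, the SD of the between-arm difference in MF-3 share is √(0.5 × 0.5 × 2/115) = 0.066, or 6.6 points. The chance of exceeding 10 points is 2 × {1 − Φ(0.10/0.066)}, about 13%.

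**Step 2: effect on the estimate.** Let g be the response rate in MF-3 minus that in lower grades. An imbalance d shifts the unadjusted difference by about d × (g_A + g_B)/2. Take control 10% (lower) and 35% (MF-3), and Arm A 23% and 55%. Then g_B = 25 and g_A = 32, and a 10-point imbalance shifts the difference by 0.10 × 28.5 = 2.85 points. Simulation agrees: 2.8 to 2.9 points unadjusted, about 0.1 after stratifying by grade. Power in that setting rose from 77.8% to 81.7% (77.6% to 80.9% in a second run).

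**Step 3: power over a range of gradients.** Simulation with 230 subjects, 1:1, common odds ratio 2.2, 4,000 runs per row, Monte Carlo error about 0.7 points. The last column is the shift in the planned estimate per 10-point excess of MF-3 in Arm A.

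| Grade mix MF-0/1/2/3 (%) | Control response by grade (%) | Overall control, treated (%) | Power, planned CMH | Power, grade added | Shift (points) |
|---|---|---|---|---|---|
| 0/10/40/50 | –/25/25/25 | 25.0, 42.3 | 79.4 | 78.1 | 0.2 |
| 0/10/40/50 | –/15/20/32 | 25.5, 42.4 | 78.8 | 78.8 | 1.7 |
| 0/10/40/50 | –/10/15/40 | 27.0, 42.9 | 72.0 | 75.2 | 3.0 |
| 0/10/40/50 | –/50/30/10 | 22.0, 36.1 | 66.7 | 70.3 | −2.7 |
| 5/15/40/40 | 0/20/25/30 | 25.0, 41.7 | 77.7 | 77.2 | 0.9 |
| 10/15/35/40 | 0/10/20/45 | 26.5, 41.1 | 65.9 | 71.7 | 3.5 |

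The change in power runs from −1.3 to +5.8 points. Separate runs with the simple split, MF-3 versus lower, gave: strong gradient 67.1% to 72.5%; reversed gradient 66.6% to 71.6%; flat 78.9% to 79.0%; 5% MF-0 but otherwise flat 75.5% to 74.8%.

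**Step 4: validity.** With no treatment effect (3,000 runs per row, Monte Carlo error about 0.4 points), the planned CMH rejected in 4.9% to 5.1% of trials. With grade added the range was 4.5% to 5.7%.

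**The case against.** The case for leaving the plan alone has real force.

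- **Nothing is invalid.** A reader might infer that omitting baseline grade biases the comparison or inflates type I error. It does neither. Under randomization the imbalance is ordinary sampling noise, already reflected in the standard error. This stands in full.
- **Room to fall is weaker than it sounds.** A reader might infer that MF-3, with three steps available, must respond more often than MF-1. The threshold is one grade, and MF-1, MF-2 and MF-3 each have that step. Only MF-0 is excluded by definition, and overt primary MF requires Grade 2 or 3 (Protocol Appendix E), so MF-0 should be rare there. No grade requirement is stated for secondary MF. Whether, and in which direction, response varies across MF-1 to MF-3 is not reported. This also stands.
- **The simple split can miss.** MF-3 versus lower pools MF-0 with MF-1 and MF-2. With 10% MF-0 and otherwise equal rates, power went from 79.5% to 78.9%; with a non-monotone pattern (45/15/25% for MF-1/2/3), from 74.6% to 73.7%. Gains need a marked gradient between MF-3 and the rest.
- **It follows the plan's convention.** SVR35 is not stratified by baseline spleen volume, nor TSS50 by baseline TSS. The contrast with the patient-reported endpoints is therefore one between binary and continuous methods, not an oversight peculiar to fibrosis.
- **Imbalance will be visible.** Baseline grade is tabulated by arm, and Protocol 7.3 allows further supportive analyses. But none is committed in advance, and an adjustment chosen after seeing an imbalance carries little weight.

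**Conclusion.** The point holds as one of precision, not validity. The ranked fibrosis test leaves out a baseline value that is already collected and that defines the response. If response depends strongly on baseline grade, a 10-point imbalance in MF-3 share moves the estimate by about 3 points (3.5 in the most extreme setting tried), and stratifying by grade raises power by about 3 to 6 points. If the dependence is weak or absent, there is no gain and a possible loss of about 1 point.

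A reader might go further and conclude that power is certainly being lost. The documents do not support that, because they give no response rates by grade. All sizes here rest on assumed grade mixes, assumed rates and 115 evaluable subjects per arm. The case for change is the asymmetry: a downside of about 1 point against an upside of 5 to 6, in a test on which four later claims depend.

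**What to change.** 1. **Reconcile SAP 8.4.1.6 first.** It counts subjects without a baseline grade, or without any later grade, as non-responders, and then restricts the analysis to subjects who have both. State one analysis set. If subjects without a baseline grade stay in, state which stratum they enter.
2. **Add the stratum.** In SAP 8.4.1.6, pre-specify baseline fibrosis grade (for example MF-3 versus lower) as a third factor in the CMH test and in the strata-adjusted difference.
3. **Keep the two-factor CMH** as a named sensitivity analysis.

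Settle this before any unblinding. Table 1 places the fibrosis test after the primary analysis, so the change should be fixed before that analysis.

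No new data are needed. Strata rise from 4 to 8, an average of 230/8 ≈ 29 subjects each, some sparser, which CMH tolerates. The work is more than a one-line edit because the missing-grade rule has to be written as well.
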